6.10.4.4 Continuous outcomes

Linear regression will be used to compare treatment groups

- Maternal glucose outcomes (HbA1c, CGM mean glucose, TIR, TAR, GMI)
- Maternal gestational weight gain (from initial antenatal visit to 36 weeks' gestation)
- Neonatal gestational age at delivery
- Birth weight SDS

Time to event outcomes: Length of hospital stay for the mother and length of hospital stay for the baby will be compared between groups using a log-rank test.

6.10.4.5 Safety evaluation

Serious Adverse Events will be tabulated by treatment group and statistical tests performed as appropriate.

6.10.4.6 Patient Reported Outcome Measures (PROMS) evaluation

Except for the Glucose Monitoring Satisfaction Survey (applicable in late pregnancy after all participants have used SMBG or CGM), questionnaire scores will be available both at baseline and at follow-up for both groups. We will compare EQ-5D summary score between randomised groups using an analysis of covariance (ANCOVA) approach. The final EQ-5D score will be the outcome variable and the baseline EQ-5D score and treatment group the co-variates. The treatment group parameter in this model estimates the treatment effect. We will summarise scores from all other questionnaires by group and the analyses will primarily be descriptive.

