5.1 Research aims

5.1.1 Research question

What is the clinical and cost-effectiveness of using continuous glucose monitoring (CGM) compared with standard care, for improving both maternal glucose and neonatal health outcomes in pregnant women with early-onset type 2 diabetes (EOT2D)?

We will examine whether using CGM improves maternal glucose and neonatal outcomes in EOT2D pregnancy. We will also measure its impact on maternal wellbeing, diabetes treatment satisfaction and cost effectiveness outcomes.

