5.2 Objectives

Our main objective is to examine whether the use of CGM relative to standard care is clinically effective, cost effective and acceptable to pregnant women with EOT2D. Specific objectives are to:

- Test the primary hypothesis that in pregnant women with EOT2D the use of real-time CGM is more effective than standard clinical care (finger-prick SMBG testing) for improving the percentage of time spent in the pregnancy target glucose range of 3.5-7.8 mmol/L and reducing clinically relevant neonatal morbidity (neonatal care admission) or perinatal death.
- Estimate the incremental use of healthcare resources, costs and impact on health-related quality of life (measured using EQ-5D-5L questionnaire) associated with CGM relative to standard care.
- 3) Assess maternal acceptability of CGM use on diabetes treatment satisfaction, health-related quality of life and maternal wellbeing outcomes using qualitative interviews and validated questionnaires.
- 4) Examine the associations between maternal glycaemia (HbA1c and CGM Time-In-Range (TIR) metrics) with obstetric and neonatal health outcomes in EOT2D pregnancy.
- 5) Assess the proportion of women with EOT2D who give consent to be contacted for future studies.

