6.5.2 Secondary outcomes

Biomedical maternal:

- HbA1c and CGM mean glucose, glucose management indicator (GMI), frequency and duration of glycaemic excursions [%Time-Above-Range (>6.7 & >7.8 mmol/L), %Time-Below-Range (<3.5 & <3.0 mmol/L)], glycaemic variability (glucose SD, CV)]
- 2) Hypertensive disorders
- 3) Gestational weight gain (from initial antenatal visit to 36 weeks' gestation)
- 4) Diabetes treatment (metformin and insulin use)
- 5) Hospital admissions and duration of stay
- 6) Severe hypoglycaemia, hyperosmolar hyperglycaemic state, and diabetic ketoacidosis episodes

Biomedical neonatal:

- 1) Gestational age at birth
- 2) Mode of delivery
- Birth weight for gestational age (SDS) (GROW customised birth weight, LGA birth weight >90th centile or SGA <10th centile)
- 4) Neonatal care unit admission (duration of stay, highest level care)
- 5) Adverse events (pregnancy loss <24 weeks, congenital anomaly (any), stillbirth, neonatal death)
- 6) Birth injury (spinal cord injury, clavicular, skull or long bone fracture, shoulder dystocia, nerve palsy, subdural or intracerebral haemorrhage confirmed by computerized tomography (CT) or magnetic resonance imaging (MRI) scan, hypoxic ischaemic encephalopathy)
- 7) Neonatal morbidity (treatment for neonatal hypoglycaemia; treatment for respiratory distress; treatment for neonatal jaundice)
- 8) Feeding at hospital discharge (exclusive breast-feeding / partial breast-feeding / exclusive formula feeding)

Patient-reported outcome measures (PROMs):

Diabetes distress, anxiety and depression and treatment satisfaction using short questionnaires at baseline (except for GMSS which is applicable only in late pregnancy) and 32 weeks' gestation:

- T2D Distress Scale (DDS)
- Glucose Monitoring Satisfaction Survey (GMSS)
- Patient Health Questionnaire 9-item depression scale (PHQ-9)
- Generalized Anxiety Disorder 7-item scale (GAD-7)
- EQ-5D-5L (maternal)

The nested qualitative study will also explore the acceptability, barriers, facilitators as well as patient and HCP support needs for CGM use in T2D pregnancy.

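### The protocol sets out to measure CGM's impact on maternal wellbeing and satisfaction, but commits to a between-arm estimate for EQ-5D only and leaves four other questionnaire outcomes primarily descriptive

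*Protocol*

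**What the plan says.** - **Aim (Protocol 5.1.1, Research question).** After the question on maternal glucose and neonatal health, the protocol adds: "We will also measure its impact on maternal wellbeing, diabetes treatment satisfaction and cost effectiveness outcomes".
- **Objective 3 (5.2).** "Assess maternal acceptability of CGM use on diabetes treatment satisfaction, health-related quality of life and maternal wellbeing outcomes". The sentence goes on to name interviews and validated questionnaires as the means.
- **Psychosocial objectives (5.2.2).** The verb is to determine distress, anxiety, depression and satisfaction. There is no between-arm wording.
- **Secondary outcomes (6.5.2).** DDS, GMSS, PHQ-9, GAD-7 and EQ-5D-5L stand together in one list, collected at baseline and 32 weeks, except that GMSS has no baseline.
- **Analysis of EQ-5D (6.10.4.6).** "We will compare EQ-5D summary score between randomised groups using an analysis of covariance (ANCOVA) approach". The covariates are baseline score and treatment group, and "The treatment group parameter in this model estimates the treatment effect".
- **Analysis of the other four (6.10.4.6).** "We will summarise scores from all other questionnaires by group and the analyses will primarily be descriptive". The same section notes that, GMSS aside, "questionnaire scores will be available both at baseline and at follow-up for both groups".
- **General model rule (6.10.4.7).** Treatment effects are to be estimated by baseline-adjusted mixed models, but the rule is worded for biomedical outcomes. The same section promises a SAP for the primary and secondary outcomes.

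**The concern.** In a randomised trial, the impact of an intervention is a contrast between arms. Five questionnaires are declared at the same level, four of them measured at the same two time points in the same women, yet only one is given that contrast.

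For the other four a reader would get scores by arm and would have to compare them by eye. There would be no interval to show how large or small a difference the data allow. For DDS, PHQ-9 and GAD-7, chance imbalance at baseline would go uncorrected although the baseline scores are in hand.

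The trial is unblinded (6.8.2) and these outcomes are self-reported. The word *primarily* also leaves room for comparisons that nobody has specified. A short, pre-stated list of estimates is safer than deciding after the data are seen which scores deserve a comparison. The outcomes matter to the trial's own case: the background section stresses anxiety and depression symptoms (36% and 14%), stigma, and the burden of glucose testing in these women.

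**Working it through.** **1. Does any section commit to a between-arm estimate for each instrument?**

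| Instrument | Secondary outcome (6.5.2) | Baseline score (6.5.2, 6.10.4.6) | Planned between-arm estimate |
|---|---|---|---|
| EQ-5D-5L | yes | yes | ANCOVA treatment effect (6.10.4.6) |
| DDS | yes | yes | none; summary by group |
| PHQ-9 | yes | yes | none; summary by group |
| GAD-7 | yes | yes | none; summary by group |
| GMSS | yes | no | none; summary by group |

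The model rule in 6.10.4.7 does not fill the gap, since it is limited to biomedical outcomes. Section 6.10.5 plans to explore how these scores relate to glucose outcomes and to engagement with CGM, which is not a contrast between arms.

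**2. The plan's own figures.** The protocol gives no sample size, power or precision for any questionnaire. The nearest figure is the analysable number in 6.7: 422 × 0.9 = 379.8, stated as 380, so 190 per arm with 1:1 allocation. The time-in-range difference that 6.7 attaches to this number reproduces: 20 × (1.960 + 1.282) × √(2/190) = 6.65 percentage points, as stated. The 380 refers to CGM profiles, so its use for questionnaires is an assumption. A lower value of 150 per arm is therefore shown as well.

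**3. Precision that the collected data would allow.** With n completers per arm and correlation r between the baseline and 32-week scores, the 95% CI half-width in SD units is

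1.96 × √[(2/n) × (1 − r²)]

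| n per arm (assumed) | r = 0 | r = 0.5 | r = 0.7 |
|---|---|---|---|
| 190 | 1.96 × √(0.01053 × 1.00) = 0.20 | 1.96 × √(0.01053 × 0.75) = 0.17 | 1.96 × √(0.01053 × 0.51) = 0.14 |
| 150 | 1.96 × √(0.01333 × 1.00) = 0.23 | 1.96 × √(0.01333 × 0.75) = 0.20 | 1.96 × √(0.01333 × 0.51) = 0.16 |

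The r = 0 column applies to GMSS, which has no baseline score. For the other three, adjustment cuts the variance by r²: 25% at r = 0.5 and 49% at r = 0.7. The protocol gives neither the correlations nor questionnaire completion.

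**4. What this shows.** The table measures the precision of the estimates that could be reported, and what baseline adjustment adds. It does not put a number on the harm of a descriptive table. Its use is to show that the design and data support a useful estimate, so the only obstacle is the analysis text in 6.10.4.6.

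**The case against.** A reader might infer that the four outcomes get only descriptive summaries, and that the trial therefore cannot estimate the impact on wellbeing. The protocol supports neither reading. It says *primarily* descriptive, and both randomised arms have 32-week scores, so the effect is estimable. EQ-5D, which has an anxiety/depression dimension (6.6.2), already gets a treatment effect, so part of wellbeing is formally covered.

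Further points on the other side:

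- **The objectives are softer than the aim.** Objective 3 speaks of acceptability and relies on "maternal wellbeing outcomes using qualitative interviews and validated questionnaires"; 5.2.2 only says determine. This stands, and it means the tension lies mainly with the sentence in 5.1.1. But the interviews cover about 20 to 25 women (6.6.4), and the schedule in 6.6 lists them for selected intervention participants, so they cannot supply a contrast with control.
- **The SAP can settle it.** A SAP is promised and may add differences with intervals. Stands in part. Section 6.10.4.6 is not silent, however: it names a method for EQ-5D and a lesser one for the rest, and a SAP that follows it inherits that split.
- **Describing unpowered, self-reported outcomes is a legitimate and open choice**, and it limits multiple testing. It is legitimate, but then the aim should not promise impact. Estimates with intervals and no p-values add no confirmatory tests.
- **EQ-5D was chosen because it also feeds the QALY analysis (6.10.6).** That explains its model. It does not make a generic instrument a measure of diabetes distress or of satisfaction with monitoring.

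**Conclusion.** The point holds as a modest mismatch between aim and analysis. The protocol says it will measure impact on wellbeing and satisfaction, lists five questionnaires as secondary outcomes, and commits to a between-arm estimate for one of them. For DDS, PHQ-9 and GAD-7 the baseline scores have no planned use for adjustment. For GMSS the 32-week contrast, the main quantitative use of a scale without a baseline, is not promised.

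The primary outcomes and the sample size are untouched. Estimates with a half-width of about 0.14 to 0.23 SD are within reach, if 150 to 190 women per arm complete the questionnaires and the baseline correlation lies between 0 and 0.7; both ranges are assumptions. The change is worth making because it costs almost nothing.

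**What to change.** In 6.10.4.6, and then in the SAP:

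1. Extend the baseline-adjusted ANCOVA planned for EQ-5D to the DDS core score, PHQ-9 and GAD-7, with the 32-week score as outcome and baseline score and treatment group as covariates.
2. For GMSS, give the between-arm mean difference at 32 weeks.
3. Report each as a mean difference with 95% CI, labelled secondary and non-confirmatory, without p-values.
4. The current EQ-5D ANCOVA does not include site, although randomisation is stratified by site (6.8.1.1). If site is added as a covariate, add it to the EQ-5D model too, so that all the models match.

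If the sponsor prefers to keep these scores descriptive, reword the aim in 5.1.1 accordingly. While editing, reconcile 6.6.2, which lists GMSS among the questionnaires completed at baseline, with 5.2.2, 6.5.2 and 6.10.4.6, which exclude it there.

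The cost is about one sentence of text and four more estimates from data already being collected. The downside is several secondary intervals without multiplicity control, which the label in step 3 makes plain.

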6.10.4.7 Statistical analysis

A detailed statistical analysis plan (SAP) for the primary and secondary outcomes will be written and approved before database lock and commencement of data analyses. We will report data in line with the Consolidated Standards of Reporting Trials (CONSORT) statement showing attrition rates and loss to follow-up. Analyses will be conducted using the intention-to-treat principle, incorporating data from all participants according to randomised group. Every effort will be made to follow up participants for outcome assessments including those who withdraw from trial interventions.

Descriptive statistics within each randomised group will be presented for baseline values. These will include counts and percentages for binary and categorical variables, and means and standard deviations (SD), or medians with lower and upper quartiles (IQR), for continuous variables, along with minimum and maximum values and counts of missing values. There will be no tests of statistical significance or confidence intervals for differences between randomised groups on baseline variables.

Treatment effects on biomedical outcomes will be estimated using linear mixed models fitted to outcome variables, adjusted for individual baseline where available, and study site as a random factor to account for potential between site differences. Where variables are measured at multiple timepoints, mixed linear models will be used to utilize data at all time points. Treatment effect on the primary neonatal endpoint will be expressed as an odds ratio with 95% CI estimated from a logistic regression model. For the primary maternal endpoint, the comparison between the two treatment arms is based on a general mixed effects regression model. The two primary endpoints will be treated as fixed effects in mixed models.

6.10.4.8 Missing data

To handle missing maternal glucose data (HbA1c or CGM) on women who withdraw from the study, we will use a multiple imputation procedure, imputing missing values from a regression model that includes earlier HbA1c or CGM values. In a sensitivity analysis, we will use an imputation procedure that assumes the data are missing-not-at-random and impute values from either the low end or high end of the observed range.

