6.7 Sample size

Assuming an anticipated neonatal care outcome incidence of 42.2% in the standard care group, based on national audit data (2, 5), a sample size of 422 would show a reduction from 42.2 to 26.0% at two-

sided 5% significance with 90% power and an assumed drop-out of 10%. An absolute reduction of 16.2% or odds ratio of 0.48 for neonatal unit admissions is based on our previous RCT data (28). The neonatal effect size in our earlier RCT (40) was higher (0.36)⁴⁰, so the most conservative estimate was chosen. A slightly smaller sample of 406 is required for the neonatal composite of neonatal admissions and death.

For the primary maternal outcome of CGM Time-in-Range (TIR) from 20 weeks until 38 weeks or delivery, 188 participants are required to detect a clinically relevant 10% increase from 60 to 70% TIR with 90% power. Using a sample size of 422 (380 analysable 14-day CGM profiles), provides 90% power to detect a CGM TIR difference of 6.65% which is deemed to be a clinically important difference. The expected maternal TIR outcome of 60% TIR (SD 20%) in the control group is based on limited EOT2D data (40-42).

The trial is powered on the neonatal unit admission outcome (involving separation of the newborn from their mother). A superiority analysis of the composite endpoint will be performed.

Sample size									
Outcome	Power	Significance	Control	Interven-	Difference	SD	Drop-	Total	
				tion			outs		
Neonatal	90%	5% (2-	42.2%	26.0%	OR 0.48	N/A	10%	422	
care		sided)			Absolute 16.2%				
Neonatal	90%	5% (2-	48.8%	31.7%	OR 0.48	N/A	10%	406	
composite		sided)			Absolute 17.2%				
CGM TIR*	90%	5% (2-	60.0%	70.0%	10.0%	20%	10%	188	
		sided)							

Table 1: Sample size estimations

*A sample size of 422 provides 90% power to detect a CGM TIR difference of 6.6% which is clinically important

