6.10.4 Statistical methods

6.10.4.1 Primary outcome analysis

Maternal glucose:

The primary analysis will evaluate the change in the time spent in the target glucose range (CGM TIR 3.5-7.8 mmol/L) between the intervention and control arm between 20 weeks' gestation and 38 weeks or until delivery (if delivered earlier), based on 4 x 14-day CGM assessments, at 20-22, 28-30, 32-34 and 36-38 weeks. The median gestation of delivery in T2D pregnancy is 38 weeks. A linear mixed effects regression model will be fit with CGM TIR from 20 weeks' gestation until delivery as the dependent variable adjusting for baseline CGM TIR, and subject as random effects. A point estimate, 95% confidence interval and p-value will be reported for the treatment effect based on the linear regression model. Residual values will be examined for an approximate normal distribution. If values are highly skewed, then a transformation or robust statistical methods will be used instead.

Neonatal outcomes:

The primary neonatal outcome is a composite of neonatal unit admission or death in line with section 6.10.4.3.

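### The missing-not-at-random check on maternal TIR fills from an unspecified end of the range, so its result turns largely on which end each arm is given

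*Protocol*

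**What the plan says.** Section 6.10.4.8 is the protocol's only missing-data rule for maternal glucose. It covers HbA1c and CGM values: "To handle missing maternal glucose data (HbA1c or CGM) on women who withdraw from the study". The main rule is multiple imputation, "imputing missing values from a regression model that includes earlier HbA1c or CGM values". The sensitivity rule assumes the data are missing not at random and is to "impute values from either the low end or high end of the observed range". It does not say which end goes to which arm, whether both arms get the same end, or whether anything between the extremes is tried.

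TIR is one of two primary outcomes (6.5.1). Its model in 6.10.4.1 is a linear mixed model "adjusting for baseline CGM TIR, and subject as random effects". Section 6.10.4.7 sets intention to treat, "incorporating data from all participants according to randomised group", and leaves further detail to a SAP. Section 6.7 plans "90% power and an assumed drop-out of 10" per cent. On TIR it says "188 participants are required to detect a clinically relevant 10% increase from 60 to 70% TIR with 90% power" and "Using a sample size of 422 (380 analysable 14-day CGM profiles), provides 90% power to detect a CGM TIR difference of 6.65" points.

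**The concern.** A sensitivity analysis of this kind should tell the reader how badly the unobserved values would have to behave before the conclusion changes. A fill from one extreme of the range answers a different question, and the answer depends on how the extremes are paired with the arms. If both arms get the same end and losses are balanced, the fills largely cancel. If the arms get opposite ends, the fills add up to a shift of several points. If losses are unequal, even the same end in both arms moves the difference, and the direction depends on the end.

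Unequal loss is plausible here. Intervention-arm training (6.6.1.2.1) says withdrawal will be considered for women who cannot show competency or compliance with CGM. Control-arm training (6.6.1.2.2) has no such clause. The trial is open label (6.8.2), so leaving the pairing of end and arm open also leaves a discretionary choice that could be made with allocation known.

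**Working it through.** **Step 1: the plan's own figures.** Inputs from section 6.7: SD 20, two-sided 5%, 90% power, 380 analysable women.

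- Detectable difference = (1.960 + 1.282) × 20 × √(4/380) = 6.65 points, as stated.
- For 10 points the calculation gives 85 per arm, 170 in total. Inflating by 1.10 gives 93.5, rounded up to 94 per arm, or 188, as stated. Dividing 170 by 0.90 gives 189.

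**Step 2: what a fill does to the difference.** Let m be the share missing, μ the observed mean and f the fill value, with subscripts I (CGM) and C (control):

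filled difference = [(1 − m_I)μ_I + m_I f_I] − [(1 − m_C)μ_C + m_C f_C]

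The protocol gives no fill values. As one assumption, take ends of 10 and 100, with μ_C = 60 and μ_I = 66.65.

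- 10% missing per arm, same end in both: 0.9 × 6.65 = 5.99 at either end.
- 10% missing, against CGM: (59.985 + 1) − (54 + 10) = −3.0.
- 10% missing, for CGM: (59.985 + 10) − (54 + 1) = 15.0.
- 5% control and 15% CGM missing, both low: (56.65 + 1.5) − (57 + 0.5) = 0.65.
- 5% control and 15% CGM missing, both high: (56.65 + 15) − (57 + 5) = 9.65.

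Milder ends (5th and 95th percentiles, about 30 and 96) at 10% missing per arm give 5.98 for the same end in both arms, −0.6 against CGM and 12.6 for CGM.

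**Step 3: simulation with fills drawn from the data.** TIR is normal with SD 20, clipped to 0–100, with 211 per arm. Fills come from the lowest or highest 5% of observed values in the same arm, and a t-test compares the arms. The true difference is 6.65.

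| Missing (control / CGM) | Fill | Difference | Significant |
|---|---|---|---|
| 10% / 10% | both low | 6.4 | about 86% |
| 10% / 10% | both high | 5.9 | about 86% |
| 10% / 10% | control high, CGM low | −1.4 | under 10% |
| 10% / 10% | control low, CGM high | 13.8 | 100% |
| 5% / 15% | both low | 2.3 | about 17% |
| 5% / 15% | both high | 9.5 | nearly 100% |

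Repeated runs moved the differences by one or two tenths of a point.

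**Step 4: does the fill always decide the matter?** No. With a true difference of 10 and 5% missing per arm, the fill against CGM gives about 5.5 and stays significant in roughly 78% of trials. At 10% missing it gives 1.9.

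**Step 5: what a graded analysis would report.** Lower the imputed CGM-arm values by δ and leave control at its missing-at-random value. At 10% missing the difference falls by 0.10 × δ. Take SE = 20 × √(2/190) = 2.05, held fixed as an approximation.

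- True 6.65: δ = (6.65 − 1.96 × 2.05)/0.10, about 26 points.
- True 10: δ = (10 − 1.96 × 2.05)/0.10, about 60 points.

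These distances can be judged for plausibility. The extreme fill does not yield them.

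**Step 6: arm in the imputation model.** If arm were left out and every withdrawal came before week 20, with only baseline known, the effect would shrink by the missing share. At 10% missing, 10 becomes 9.0 and 6.65 becomes 6.0. In a simulation of a baseline and four visits, with withdrawals spread over the visits (within-woman correlation 0.5 or 0.7), 10 becomes 9.7 and 6.65 becomes 6.5. With arm included, the effect is recovered (9.98 to 10.12 and 6.63 to 6.78).

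**The case against.** **Extreme-case bounds are legitimate.** A low-end or high-end fill is crude, but it is a recognised missing-not-at-random bound, and it responds to the data. At a true 6.65 with the same end in both arms, significance is about 86%, close to the 89% without any fill. When losses are unequal, a same-end fill does pick up the imbalance. This stands. A reader might infer that the check has a foregone answer, always passing one way and always failing the other. Step 4 shows that it does not.

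**The rest is SAP detail.** Pairing ends with arms could be settled in the SAP, which is not shown. That is fair for the pairing. The method itself is fixed in the protocol, however, and a pairing alone would not supply the intermediate values.

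**Arm in the imputation model.** A reader might infer that the protocol imputes without treatment arm and so biases the primary result toward zero. The text does not support this. It says what the model includes and does not exclude arm, and predictor lists are ordinary SAP content. Even if arm were omitted, the loss would be about 3% to 10% of the effect at 10% missing.

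**The simulation is simpler than the plan.** It uses one TIR value per woman and a t-test, where the protocol plans a baseline-adjusted mixed model over four 14-day profiles. Women who stop only the intervention are also asked to stay in follow-up with masked sensors (6.4.6, 6.6.5), which may keep missingness below 10%. The sizes are therefore illustrative. The dependence on end and arm follows from the formula in Step 2.

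**Conclusion.** The point holds in a limited form. The stated sensitivity analysis can move a true 6.65-point TIR difference to anywhere from about −1.4 to 13.8 at the planned 10% loss, depending on how ends are paired with arms. With an assumed 5%/15% split of losses, it gives about 2.3 or 9.5 depending on the end alone. It does not show how large a departure from missing at random the conclusion can bear.

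The assumptions that are not in the protocol are the definition of an end (extreme 5%, or the alternatives in Step 2), the split of losses by arm, normality, and one value per woman. The amount of missing data and the true effect matter too, so the choice of end is a large influence and not the only one.

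This concerns a sensitivity analysis. The primary TIR analysis is not shown to be wrong, and the trial is sized on neonatal unit admission (6.7). It is a cheap improvement worth making before data are seen.

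**What to change.** In section 6.10.4.8, replace the low-end/high-end fill with a delta-adjusted tipping-point analysis:

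- Start from the missing-at-random imputations.
- Lower the imputed TIR in the CGM arm in stated steps (2.5 points, for example), leaving control unchanged.
- Then vary the shift in both arms over a stated grid.
- Report the delta at which the 95% CI first includes zero, and say whether a shift of that size is plausible.

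When the SAP is written, name randomised arm as a predictor in the imputation model, together with baseline and earlier TIR and HbA1c.

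The cost is a change of wording and a short program, with no new data. The downside is that a grid of results is reported instead of one or two fills.
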